5.1.2 Handling of missing items for scales

If any of the individual items for the MDS-UPDRS Part II and MoCA is missing, the total score of the corresponding endpoint will be imputed by prorating the observed scores [van Ginkel 2010].

- For MDS-UPDRS Part II, if 3 or fewer of 13 items (<25%) are missing, the total score will be imputed by the prorating algorithm. If more than 3 items are missing, the total score of MDS-UPDRS Part II at that visit will be considered missing.
- For MoCA, if 1 domain (<25%) of the 7 domains is missing, the total score will be imputed using the same prorating algorithm; if more than 1 domains are missing, the total score at that visit will be considered as missing.

For CTT 1 and 2, if any test scores are missing due to participant too impaired, participant refused, refusal (subject or informant), physical reason, or too impaired (cognitively or psychiatrically), the missing values will be imputed to 240 seconds. If subjects failed the CTT pretest (hence no CTT was assessed), or did not complete CTT within the time limit of 240 seconds, the missing values will be imputed to 240 seconds as well.

For Letter number sequence test, if partial item scores are missing due to participant too impaired, participant refused, refusal (subject or informant), physical reason or too impaired (cognitively or psychiatrically), the missing LNS total raw score will be imputed with the sum of completed item scores, and the longest LNS total raw score will be imputed with the count of longest sequence (string) numbers and letters correctly reproduced by participant.

For each of the individual component tests in the PSP cognitive composite battery, if partial item scores within a test are missing due to participant too impaired, participant refused, refusal (subject or informant), physical reason, or too impaired (cognitively or psychiatrically), the missing test score will be imputed using the sum of completed item scores.

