5.3.1.1 Primary analysis of MDS-UPDRS Part II

The MDS-UPDRS Part II includes 13 items assessing motor aspects of experiences of daily living. These include speech, saliva and drooling, chewing and swallowing, handwriting, doing hobbies and other activities, eating tasks, tremor, dressing, hygiene, turning in bed, getting out of bed, walking and balance, and freezing. Each individual item has a 5-point scale, ranging from 0 to 4: 0 for “Normal”; 1 for “Slight”; 2 for “Mild”; 3 for “Moderate”; and 4 for “Severe”. The total score is calculated by adding all required item scores, and ranges from 0 to 52.

The primary analysis of change from baseline MDS-UPDRS Part II scores will be based on the base MMRM model described in Section 5.1. A line plot of adjusted mean change from baseline over time and a bar plot of adjusted mean change from baseline at Week 52 will be provided.

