5.3.2.5 Color Trails Test

The CTT is a language-free version of the Trail Making Test and was developed to allow for broader cross-cultural assessment. The form consists of two parts, CTT 1 and CTT 2.

For CTT 1, the participant simply has to connect the numbered circles, in order, from 1 to 25, by drawing a continuous line from circle to circle.

For CTT 2, the test demand is the same, except the participant must alternate between colors while connecting the circles.

The score for each part of the test is the total time required for completion in seconds. The maximum time allowed for each test trial is 240 seconds.

The primary analysis of change from baseline CTT 1 will be based on the base MMRM model described in Section 5.1.

The primary analysis of change from baseline CTT 2 will be based on the base MMRM model described in Section 5.1 along with removing the CTT 2 factor in the model.

5.3.2.6 **MoCA**

The MoCA is a one-page 30-point test designed as a rapid screening instrument for mild cognitive dysfunction. Scores for 8 cognitive domains are calculated: visuospatial/executive (maximum of 5 points); naming (maximum of 3 points); memory (total number of words remembered correctly across 2 trials; no points); attention (sum of scores for 3 questions; maximum of 6 points); language (sum of scores for 2 questions; maximum of 3 points); abstraction (maximum of 2 points); delayed recall (maximum of 5 points); orientation (maximum of 6 points). The total score is calculated by summing all domain scores (excluding memory) and adding a point for participant's education level ≤ 12 years. The maximum total score is 30 points; a score of 26 or above is considered normal.

The primary analysis of change from baseline MoCA total scores will be based on the base MMRM model described in Section 5.1.

5.3.2.7 **RBANS**

The RBANS was developed for the dual purposes of identifying and characterizing abnormal cognitive decline in the older adult. The full battery is composed of 12 subtests: List Learning; Story Memory; Figure Copy; Line Orientation; Picture Naming; Semantic Fluency; Digit Span; Coding; List Recall; List Recognition; Story Recall; and Figure Recall. Five Sum of Index Scores are calculated from the 12 subtests:

- List Learning and Story Memory
- Figure Copy and Line Orientation
- Picture Naming and Semantic Fluency
- Digit Span and Coding
- List Recall, List Recognition, Story Recall and Figure Recall

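### The MoCA proration rule gives no formula; on its natural reading it scales by number of domains, which does not suit domains worth 2 to 6 points

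*SAP*

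**What the plan says.** Section 5.1.2 of the placebo-controlled SAP covers missing items on two scales together. For MDS-UPDRS Part II and MoCA, "the total score of the corresponding endpoint will be imputed by prorating the observed scores", with a literature citation but no formula. The two scales then get their own conditions:

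- MDS-UPDRS Part II: "if 3 or fewer of 13 items (<25%) are missing, the total score will be imputed by the prorating algorithm".
- MoCA: "For MoCA, if 1 domain (<25%) of the 7 domains is missing", then "the total score will be imputed using the same prorating algorithm". With more than one domain missing, the total is missing.

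The scales are built differently. For MDS-UPDRS Part II, Section 5.3.1.1 says: "Each individual item has a 5-point scale, ranging from 0 to 4". For MoCA, Section 5.3.2.6 lists seven scored domains with maxima of 5 (visuospatial/executive), 3 (naming), 6 (attention), 3 (language), 2 (abstraction), 5 (delayed recall) and 6 (orientation). The eighth, memory, carries no points. One point is added for 12 years of education or less. "The maximum total score is 30 points; a score of 26 or above is considered normal".

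Section 5.1.2 does not weight domains by their maxima, set a cap, or say whether the education point is added before or after prorating.

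**The concern.** Prorating by count fills a missing component with the average of the observed ones. That is sound when all components share the same range, as the MDS-UPDRS Part II items do. Carried over to MoCA, a factor of 7/6 treats every missing domain as worth 30/7 = 4.29 points. No domain is worth that, so the total is mis-scaled upwards when a small domain is missing and downwards when a large one is.

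MoCA is analysed as change from baseline with the base MMRM (Sections 5.1.4 and 5.3.2.6). An error in an imputed total therefore passes undiluted into that visit's change score, and an imputed baseline total carries its error into every change score for that participant. An imputed total can also be one that the participant could not have reached whatever the missing domain would have shown.

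**Working it through.** **Inputs.** Domain maxima, scale maximum and education point come from Section 5.3.2.6; the rule and its thresholds from Section 5.1.2; the MDS-UPDRS item range from Section 5.3.1.1.

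**The plan's own figures.** 5 + 3 + 6 + 3 + 2 + 5 + 6 = 30, as stated. 1/7 = 14.3% and 3/13 = 23.1%, both below 25% as stated.

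**Two readings of the rule.** S is the observed sum over six domains and m the maximum of the missing domain.

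- By count: imputed total = S × 7/6.
- By points: imputed total = S × 30/(30 − m).

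For MDS-UPDRS Part II the two coincide because every item has a maximum of 4. For MoCA they differ for every domain.

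**Systematic error of the count reading.** Assume the participant scores the same proportion p of the points in every domain. Then S = p(30 − m), the true total is 30p, and

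error = p(30 − m) × 7/6 − 30p = p × (5 − 7m/6).

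| Missing domain | m | Imputed total at p = 1 | Error, p = 1.0 | Error, p = 0.8 | Error, p = 0.6 |
|---|---|---|---|---|---|
| Abstraction | 2 | 32.67 | +2.67 | +2.13 | +1.60 |
| Naming or language | 3 | 31.50 | +1.50 | +1.20 | +0.90 |
| Visuospatial/executive or delayed recall | 5 | 29.17 | −0.83 | −0.67 | −0.50 |
| Attention or orientation | 6 | 28.00 | −2.00 | −1.60 | −1.20 |

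An error of 2 points or more needs abstraction missing with p ≥ 2/2.667 = 0.75, or a 6-point domain missing at p = 1 (exactly 2.0).

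**Totals above 30.** S × 7/6 > 30 needs S > 180/7 = 25.7, so S ≥ 26 (26 × 7/6 = 30.33). Before any education point, this can happen only with abstraction missing (S up to 28) or with naming or language missing (S up to 27). With the education point and no cap, the ceiling with abstraction missing is 28 × 7/6 + 1 = 33.67 if the point is added afterwards, or 29 × 7/6 = 33.83 if it is prorated too. With a 5-point domain missing, the corresponding values are 30.17 and 30.33.

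**Unattainable totals.** This check needs no assumption about p. The count reading adds S/6 for the missing domain, and the domain can contribute at most m. The imputed total is unattainable when S/6 > m:

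- abstraction missing: S > 12 (of 28);
- naming or language missing: S > 18 (of 27);
- a 5- or 6-point domain missing: never, since S is at most 25 or 24.

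Example: abstraction missing and S = 23 gives 23 × 7/6 = 26.83, although the participant could have scored at most 25. The imputed total lies above the normal cut of 26 and the highest possible total lies below it.

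**Points reading.** p(30 − m) × 30/(30 − m) = 30p. The systematic error is 0 for every domain and every p, and the prorated sum cannot exceed 30.

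**The case against.** The strongest objection is that the factor 7/6 appears nowhere in the SAP. The counts in Section 5.1.2 are conditions for when imputation is allowed, not multipliers. Prorating by points also fits the wording, and since the two methods agree for MDS-UPDRS Part II, calling the MoCA algorithm the same does not decide between them. This stands to the extent that the text does not specify the formula. Counting is still the natural reading. The MoCA condition is expressed in domains, and two missing domains (2/7 = 28.6%) set the total to missing, although by points abstraction plus naming is only 5/30 = 16.7% and naming plus language 6/30 = 20%. If points were intended, the SAP still needs to say so.

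A reader might also infer four stronger things that the documents do not support.

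- **That the imputed total is wrong whichever domain is missing.** The error table assumes equal proportional performance. With visuospatial/executive missing at a true score of 4 and 24 of 25 on the rest, 24 × 7/6 = 28 is exact, while prorating by points gives 24 × 30/25 = 28.8. Either method can miss an individual score; the advantage of points is the absence of systematic mis-scaling.
- **That errors of 2 to 3 points are typical.** They are the upper end. For the other four domains (naming, language, visuospatial/executive, delayed recall) the systematic error is at most 1.5 points even at ceiling.
- **That the error tracks disease severity**, because drawing or speech tasks are missed more often in PSP. Neither document says which domains are missed or why.
- **That the treatment comparison is biased.** The same rule applies in both arms, the sign of the error varies by domain, and the documents give no frequency of single-domain gaps.

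The reach is also limited. MoCA is a non-key secondary endpoint with nominal p-values (Section 5.3.2). The open-label extension SAP adopts the same imputation method, but its interim efficacy analysis is confined to the primary and key secondary endpoints and so leaves MoCA out.

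**Conclusion.** The point holds as a small correction. The rule is under-specified, and its most natural reading is unsuitable for MoCA. The size of the systematic error depends on two assumptions: that the total is scaled by 7/6, and that participants score the same proportion in each domain. The finding of unattainable totals depends only on the first of these. Totals above 30 are confined to near-ceiling scorers, whereas unattainable totals below 30 are not.

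Nothing here touches the primary or key secondary results. The consequence is limited to MoCA totals at visits with exactly one missing domain, and no effect on the between-arm difference has been shown.

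**What to change.** Replace the MoCA bullet in Section 5.1.2 with an explicit rule: if one of the seven scored domains is missing, imputed total = observed domain sum × 30/(30 − maximum of the missing domain); add the education point after prorating; cap the total at 30. With abstraction missing this gives 30.00 instead of 32.67 at ceiling and 24.00 instead of 26.13 at 80%. With attention or orientation missing it gives 24.00 instead of 22.40 at 80%.

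The same edit should say what happens when a domain is only partly missing. Section 5.1.2 opens with missing items but the MoCA condition is about missing domains, and attention has three questions and language two.

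The cost is a line or two of SAP text and the matching derivation code. No data collection, sample size or testing order changes, and the MDS-UPDRS Part II rule can stay as it is.

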5.1.3 Considerations for multiple comparison adjustments

Key secondary endpoints have been rank prioritized, in the order shown in Section 2. In order to control for a Type I error for the key secondary endpoints, a sequential closed testing procedure will be used. If statistical significance is not achieved for a key secondary endpoint, all key secondary endpoint(s) of a lower rank will not be considered statistically significant.

There will be no multiple comparison adjustments for the sensitivity or supplementary analyses for the primary and key secondary efficacy endpoints, the non-key secondary endpoints, the tertiary efficacy endpoints, the subgroup analyses or the additional analyses.

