2 DESCRIPTION OF OBJECTIVES AND ENDPOINTS

The objectives and endpoints from the protocol Section 4 are described below.

| Objective | Endpoint |
|---|--|
| Primary | |
| To evaluate the efficacy of BIIB092, compared to placebo, as measured by a change from baseline in the PSP Rating Scale (PSPRS) at Week 52. | The primary efficacy endpoint will be evaluated by comparing the change from baseline in the total PSPRS score at Week 52 in participants treated with BIIB092 relative to the change from baseline in the total PSPRS score in participants treated with placebo. |
| To assess the safety and tolerability of BIIB092, relative to placebo, by measuring the frequency of deaths, SAEs, and AEs leading to discontinuation, and Grade 3 & 4 laboratory abnormalities. | The primary safety endpoint will be evaluated by tabulating the numbers and percentages of deaths and unique participants with SAEs and AEs leading to discontinuation, and Grade 3 & 4 laboratory abnormalities. |
| Key Secondary | |
| To evaluate the efficacy of BIIB092, compared to placebo, as measured by a change from baseline in the Movement Disorder Society-sponsored revision of the Unified Parkinson's Disease Rating Scale (MDS-UPDRS) Part II at Week 52. | The impact of BIIB092 on the MDS-UPDRS Part II will be evaluated relative to the change from baseline at Week 52 in the BIIB092-treated participants and compared to that of the placebo-treated participants. |
| To evaluate the efficacy of BIIB092, compared to placebo, as measured by the Clinical Global Impression of Change (CGI-C) at Week 52. | The impact of BIIB092 on the CGI-C scale score will be evaluated at Week 52 in the BIIB092-treated participants and compared to that of the placebo-treated participants. |
| To evaluate the efficacy of BIIB092, compared to placebo, as measured by a change from baseline in the Repeatable Battery for the Assessment of Neuropsychological Disease Severity (RBANS) at Week 52. | The impact of BIIB092 on the RBANS scale will be evaluated relative to the change from baseline at Week 52 in the BIIB092-treated participants and compared to that of the placebo-treated participants. |

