5.3 Secondary Efficacy Endpoints

5.3.1 Key Secondary Efficacy Endpoints

The key secondary endpoints include MDS-UPDRS Part II, CGI-C, PSP cognitive composite battery and PSP-QoL. The sequential test described in Section 5.1 will be used to test the key secondary endpoints in the following order: MDS-UPDRS Part II, CGI-C, PSP cognitive composite battery, PSP-QoL physical scale, PSP-QoL mental scale and PSP-QoL VAS. An overall summary of all key secondary endpoints will be provided. A line plot of adjusted mean change from baseline over time and a bar plot of adjusted mean change from baseline at Week 52 will be provided for all key secondary endpoints with the exception for CGI-C where only adjusted mean will be used. Listings will be provided for all secondary efficacy endpoints.

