5.3.1.3 Primary analysis of PSP cognitive composite battery

The PSP cognitive composite battery will be used to identify and characterize abnormal cognitive decline in PSP subjects. The PSP cognitive composite battery includes 13 sub-tests in total: 11 tests from the RBANS (only the picture naming is excluded), letter number sequencing test, and phonemic fluency test. The factor analysis suggested three domains:

- Memory and learning: List Learning, Story Memory, List Recall, List Recognition and Story Recall
- Visual-Motor function: Figure Copy, Coding and Figure recall
- Working memory and Executive: Semantic Fluency, Digit Span, Line Orientation, Letter Number Sequencing test and Phonemic Fluency test

For each of the 13 sub-tests, a z-score will be calculated based on scores from baseline data of PASSPORT study. [REDACTED]

[REDACTED]

[REDACTED]

[REDACTED]

[REDACTED]

The z-score for each domain is calculated as the sum of z-scores of the completed tests divided by the number of tests completed. A final total composite z-score of the PSP cognitive composite battery is calculated as the average of three domain z-scores. If there are any missing values for domain z-scores, then no final composite z-score will be calculated.

The RBANS is collected at Weeks 0, 12, 24, 36, and 52, while the letter number sequence test and phonemic fluence test are collected at Weeks 0, 12, 24, 36, and 48. The windowing rule of RBANS (Section 5.1.1 Table 3) will be applied to all sub-tests.

The composite z-score will be used for the primary analysis of the PSP cognitive composite battery using the base MMRM model described in Section 5.1. A line plot of adjusted mean change from baseline over time will also be provided.

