5.3.1.4 Primary analysis of PSP-QoL

The PSP-QoL is a participant-reported outcome measure developed specifically for assessing the health-related quality of life in people living with PSP. It is a validated 45-item questionnaire and visual analog scale that is comprised of two subscales: physical health state (22 items), which covers mobility, dysarthria, dysphagia, visual disturbances, self-care, and activities of daily living, and mental health state (23 items), which covers emotional, cognitive and social functioning. Items are given a 6-reponse option format (No Problem, Slight Problem, Moderate Problem, Marked Problem, Extreme Problem and Not Applicable). The subscale results are calculated from summing the respective items for that subscale and transforming the scores into a range of 0 to 100, with higher scores indicating a greater impact of the disease on the aspect measured. The transformation algorithm for physical and mental scales is $100 * (\text{observed score} - \text{minimal possible score}) / (\text{max possible score} - \text{minimal possible score})$ where the minimal possible score is 0.

The PSP-QoL also comprises of a Life Satisfaction rating gauge, which is a visual analog scale with a range of 0 (worst) to 100 (best).

The primary analysis of change from baseline PSP-QoL physical scale, mental scale and life satisfaction rating scale scores will be based on the base MMRM model described in Section 5.1. A line plot of adjusted mean change from baseline over time will be provided.

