5.3.2 Non-Key Secondary Efficacy Endpoints

Non-key secondary endpoints are tested at an uncontrolled alpha level of 0.05 per endpoint. The P values resulting from these analyses are considered as nominal and descriptive in nature.

Sections 5.3.2.1 through 5.3.2.6 provide additional details about the efficacy assessments.

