The total scale score is calculated from the 5 Index Scores which will be used for the primary analysis of RBANS. The primary analysis of change from baseline RBANS scores will be based on the base MMRM model described in Section 5.1. A line plot of adjusted mean change from baseline over time will be provided. A listing will also be generated.

For the 5 RBANS index scores, the baseline value and the change from baseline at each post-baseline visit will be summarized by treatment group. The same MMRM model as the primary analysis will also be applied to the 5 sum of index scores.

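### The placebo-controlled SAP gives two different orders for testing the key secondary endpoints, and they diverge from rank 3

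*SAP*

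**What the plan says.** All sections cited are in the placebo-controlled SAP unless stated otherwise.

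- **Section 5.1.3** sets the multiplicity rule. It uses a sequential closed procedure in which a failure at one rank bars every lower rank from significance. The ranking is given only by cross-reference: "Key secondary endpoints have been rank prioritized, in the order shown in Section 2".
- **Section 2** introduces its table with "The objectives and endpoints from the protocol Section 4 are described below". Its key secondary rows are MDS-UPDRS Part II, CGI-C, the "Repeatable Battery for the Assessment of Neuropsychological Disease Severity (RBANS) at Week 52", and PSP-QoL as one entry with no subscale named. Protocol 17.4.1 gives the same four-step order.
- **Section 5.3.1** says that the sequential test of Section 5.1 will be run "in the following order: MDS-UPDRS Part II, CGI-C, PSP cognitive composite battery, PSP-QoL physical scale, PSP-QoL mental scale and PSP-QoL VAS".
- **Section 5.3.1.3** builds the cognitive composite from 13 subtests: "11 tests from the RBANS (only the picture naming is excluded"), plus letter-number sequencing and phonemic fluency. The score is the average of three domain z-scores.
- **Section 5.3.1.4** analyses "change from baseline PSP-QoL physical scale, mental scale and life satisfaction rating scale scores". It defines no PSP-QoL total.
- **Section 5.3.2** states that "Non-key secondary endpoints are tested at an uncontrolled alpha level of 0.05 per endpoint" and treats those p-values as nominal. RBANS falls under this heading, in 5.3.2.7: "The total scale score is calculated from the 5 Index Scores which will be used for the primary analysis of RBANS".

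**The concern.** A fixed-sequence procedure protects the type I error because one order is fixed before the data are seen. Here one procedure has two orders, and no readable text says which takes precedence. The sentence that governs multiplicity selects the list that the analysis sections do not use.

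The two third-ranked endpoints are different measures. RBANS total is built from five index scores over 12 subtests. The composite drops picture naming, adds two tests from outside RBANS and is scored as an average of domain z-scores. One can reach significance when the other does not.

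Rank 3 decides whether any PSP-QoL result can be claimed as confirmatory. Under 5.1.3 as written, RBANS total would open PSP-QoL although 5.3.2 treats it as nominal. The next step would then be a single PSP-QoL test that the SAP does not define.

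**Working it through.** **The two orders side by side**

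| Rank | Section 5.1.3 via Section 2 (and protocol 17.4.1) | Section 5.3.1 |
|---|---|---|
| 1 | MDS-UPDRS Part II | MDS-UPDRS Part II |
| 2 | CGI-C | CGI-C |
| 3 | RBANS | PSP cognitive composite battery |
| 4 | PSP-QoL (one entry) | PSP-QoL physical |
| 5 | none | PSP-QoL mental |
| 6 | none | PSP-QoL VAS |

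Ranks 1 and 2 agree, and the lists part at rank 3.

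**The plan's own figure.** Protocol 17.4.1 states an overall type I error of 0.05 with 0.05 at each level. This holds for either list taken alone. In a fixed sequence a false claim requires rejecting the first true null reached, and that has probability at most 0.05. The same argument covers the case where the primary, rank 1 or rank 2 is truly null: a false claim must then begin at a step common to both lists, so the family-wise error stays at or below 0.05 under either.

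**How often the choice of list matters.** Condition on the primary and ranks 1 and 2 having passed, and treat those gates as uninformative about rank 3. Let Z1 and Z2 be the test statistics for RBANS total and the composite, bivariate normal with correlation r, and let z = 1.96. The documents give no r, so a range is used. The 11 shared subtests favour the high end.

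*(a) Disagreement on whether PSP-QoL opens.* With equal power p, each statistic has mean 1.96 + Φ⁻¹(p). The probability that exactly one exceeds z is 2 × [p − P(both > z)].

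| r | P(both), p = 0.80 | Disagree | P(both), p = 0.50 | Disagree |
|---|---|---|---|---|
| 0.95 | 0.765 | 0.071 | 0.449 | 0.101 |
| 0.90 | 0.750 | 0.100 | 0.428 | 0.144 |
| 0.80 | 0.729 | 0.142 | 0.398 | 0.205 |
| 0.70 | 0.713 | 0.174 | 0.373 | 0.253 |

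For example, at p = 0.80 and r = 0.90: 2 × (0.80 − 0.750) = 0.100.

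*(b) Both cognitive nulls true and the list chosen after unblinding.* The false rank-3 claim rate is P(|Z1| > z or |Z2| > z). In the favourable direction only, it is P(Z1 > z or Z2 > z), against a nominal 0.025.

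| r | Two-sided | Favourable direction |
|---|---|---|
| 0.95 | 0.065 | 0.032 |
| 0.90 | 0.070 | 0.035 |
| 0.80 | 0.078 | 0.039 |
| 0.70 | 0.083 | 0.042 |

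Case (b) bounds what an unfixed order would allow. It is not an error rate that the plan implies.

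**The case against.** The strongest reply is that 5.3.1 is plainly the operative list and 5.1.3 merely has an out-of-date cross-reference. The evidence for this is good:

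- Table 1 has rows for the composite and none for RBANS.
- The title of Table 3 names RBANS outside the key set.
- Sections 5.3.1.3 and 5.3.1.5 treat the composite as key, and Section 5.3 of the open-label extension SAP names it among the key secondaries.
- Section 2 restates the protocol and does not mention the 15-item PSPRS, which Section 5.2 makes the US primary endpoint. It was evidently not updated.

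On this view the three PSP-QoL scores refine the single Section 2 entry, since no passage gives a competing order for them. The probabilities above would then describe a choice that nobody proposes to make. The contents also list a section on changes from Version 1 (Section 10), which is not readable here and may record the switch.

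Most of this stands. The intended order can be recovered, the PSP-QoL split is mainly a refinement, and the figures are conditional illustrations. The reply does not remove the conflict at rank 3. Protocol 17.4.1 and the SAP's own multiplicity section both put RBANS there, so anyone checking a confirmatory PSP-QoL claim against those two places would find the wrong gate. An entry in Section 10 could explain the change but would leave the sentence in 5.1.3 as it is.

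**Conclusion.** The concern holds. As written, the rule in 5.1.3 contradicts 5.3.1 from rank 3 down and cannot be carried out literally, because it leads to a PSP-QoL test that is not defined. That 5.3.1 is the intended list is inferred from the rest of the SAP, which does not say so.

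The effect is limited to confirmatory claims on cognition and PSP-QoL, and only if the primary and ranks 1 and 2 succeed. Within that setting the lists give different answers on opening PSP-QoL in 7% to 17% of trials at 80% power and 10% to 25% at 50% power. Those ranges assume equal power for the two cognitive measures and correlations from 0.95 down to 0.7. Neither list inflates the error rate once it is fixed. This should be corrected, but it does not threaten the trial's main result.

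**What to change.** Before unblinding:

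1. In 5.1.3, replace the reference to Section 2 with the order in 5.3.1: MDS-UPDRS Part II, CGI-C, PSP cognitive composite battery, PSP-QoL physical, PSP-QoL mental, PSP-QoL VAS.
2. In Section 2, change the cognitive and PSP-QoL key secondary rows to match, and list RBANS total as non-key.
3. Record the departure from protocol 17.4.1, with its reason, unless Section 10 already does so.

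The cost is one sentence, two table rows and, if needed, a note of the change. Nothing changes in the data collected, the sample size or the alpha.
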